4.0 Analysis Population

The following population sets will be used for the analyses.

The intent-to-treat (ITT) population consists of all randomized subjects. The ITT population will be used for baseline analyses. Subjects will be included in the analysis according to the randomized study intervention.

The safety population consists of all subjects who received at least 1 administration of study intervention. Subjects will be summarized according to the study intervention they actually received.

For all analyses, vehicle groups will be pooled for Stage 1 and Stage 2a separately.

5.0 Subject Disposition

The number of subjects screened for the study will be provided.

The summary of study disposition post randomization will be provided in total and by study intervention for the following:

- Number of subjects randomized (this frequency count will be used as the denominator to calculate the percentages described below)
- Number and percentage of subjects treated
- Number and percentage of subjects who completed the study
- Number and percentage of subjects who discontinued the study
- Reasons for discontinuation from the study

6.0 Study Treatment Duration

For Stage 2a, exposure to the study treatment will be summarized for treatment duration, calculated as the number of days from the date of the first dose of study intervention to the date of the last dose of study intervention, inclusive. Descriptive statistics will be presented.

7.0 Subject Characteristics

Categorical variables will be summarized with the number and percentage of subjects. Continuous variables will be summarized with descriptive statistics (number of non-missing observations, mean and standard deviation, median, minimum and maximum).

7.1 Demographics and Baseline Characteristics

Demographic parameters (age; age group (≤ 50 , > 50); sex; race; ethnicity) will be summarized in total and by study intervention.

8.0 Safety Analyses

8.1 General Considerations

Safety data will be summarized for the safety population. Safety summaries will be presented by the treatment group for Stage 1 and 2a, respectively.

Vehicle groups will be pooled for Stage 1 and Stage 2a separately.

8.2 Adverse Events

8.2.1 Treatment-Emergent Adverse Events

An AE will be considered a treatment-emergent adverse event (TEAE) if the AE began or worsened (increased in severity or became serious) on or after the first administration of study intervention.

A treatment-emergent serious adverse event (TESAE) is defined as a serious adverse event (SAE) that is also TEAE.

Ocular adverse events include those with locations noted by the investigator as OD or OS on the CRF.

8.2.2 Adverse Event Overview

An overview of AEs will be presented consisting of the number and percentage of subjects experiencing at least one event by study intervention group for each cohort for below summaries. Additional summaries may be provided when applicable.

- TEAEs
 - Ocular
 - Nonocular
- Treatment-related TEAEs
 - Ocular
 - Nonocular

- Deaths
- TESAEs
 - Ocular
 - Nonocular
- Treatment-related TESAEs
 - Ocular
 - Nonocular
- TEAEs leading to discontinuation from study
 - Ocular
 - Nonocular

8.2.3 Treatment-Emergent Adverse Events by SOC and/or PT

Treatment-emergent adverse events will be summarized by SOC and PT. Specific adverse events will be counted once for each subject for calculating percentages, except for ocular AE, which is counted once for each eye.

- Ocular TEAEs by primary SOC and PT
- TEAEs by primary SOC, PT, and severity

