9.4.2. Safety Analyses

The safety analyses will be performed using the safety population and will be fully defined in the SAP. The safety parameters will include AEs, vital signs, 12-lead ECG, and clinical laboratory assessments. Other safety parameters will be defined in the SAP.

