9.4.2.1. Adverse Events

An AE will be considered a TEAE if the AE began or worsened (increased in severity or became serious) on or after the date of the first dose of study intervention. However, an AE that occurs more than 30 days after the last dose of study intervention will not be counted as a TEAE.

An AE will be considered a TESAE if it is a TEAE that additionally meets any SAE criterion.

For each study cohort, the number and percentage of participants reporting TEAEs during the study will be tabulated by system organ class and preferred term and by system organ class, preferred term, and severity. AE assessments will be presented by cohort and study intervention.

If more than one AE is coded to the same preferred term for the same participant, the participant will be counted only once for that preferred term using the most severe and most related occurrence for the summarizations by severity and by relationship to study intervention.

Summary tables will be provided for participants with SAEs and participants with AEs leading to discontinuation if 5 or more participants reported such events. Listings of all AEs, SAEs, and AEs leading to discontinuation by participant will be presented.

The definitions of an AE and SAE can be found in Appendix 3, Section [10.3](#).

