8.2.4 Adverse Events Leading to Study Treatment Discontinuation

Listings of TEAEs leading to discontinuation will be presented.

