8.3 Analysis of Laboratory Data

Descriptive statistics for values and changes from baseline in standard units at each assessment timepoint will be summarized.

Clinical laboratory test values will be considered potentially clinically significant (PCS) if they meet either the lower-limit or higher-limit PCS criteria listed in Appendix B. The number and percentage of subjects who have at least one PCS postbaseline clinical

laboratory value will be tabulated. The denominator will be the number of subjects with available non-PCS baseline values and at least 1 postbaseline value. The numerator will be the number of subjects with available non-PCS baseline values and at least 1 PCS postbaseline value.

Subjects with PCS findings will be listed.

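### Ocular adverse events are counted per eye with no stated denominator or table scope, so participant incidence by ocular preferred term in Stage 2a may appear in no table

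*SAP*

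**What the plan says.** SAP section 8.2.3 states the rule "Specific adverse events will be counted once for each subject for calculating percentages, except for ocular AE, which is counted once for each eye". Two tables follow it: ocular TEAEs by system organ class and preferred term, and all TEAEs by system organ class, preferred term and severity. The rule stands above both and is not limited to either. Section 8.2.1 defines the ocular category: "Ocular adverse events include those with locations noted by the investigator as OD or OS on the CRF".

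Protocol section 9.4.2.1 uses the participant as the unit. For each cohort, "the number and percentage of participants reporting TEAEs during the study will be tabulated by system organ class and preferred term", and again with severity added. A participant with several events under one term is "counted only once for that preferred term using the most severe and most related occurrence for the summarizations by severity". There is no exception for ocular events. The same section promises listings: "Listings of all AEs, SAEs, and AEs leading to discontinuation by participant will be presented".

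Protocol section 9.4.2 leaves the detail to the SAP: "The safety analyses will be performed using the safety population and will be fully defined in the SAP". SAP section 12.1 says that changes from the protocol analysis are set out in Table 3. That table records the loss of Stage 2b and the narrowing of output to the main safety analyses. It records no change of counting unit.

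**The concern.** Three things are left open.

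- **Denominator.** The rule concerns percentages, yet nothing says what an eye count is divided by. The safety population is defined in subjects. The SAP can be exact about this: for laboratory values in section 8.3 it writes "The denominator will be the number of subjects with available non-PCS baseline values and at least 1 postbaseline value".
- **Scope.** Under reading A (literal, both tables), the severity table mixes eye counts for ocular terms with subject counts for the rest. A participant whose two eyes differ in severity falls in two severity rows, and no table in the SAP gives participant incidence by ocular term. Under reading B (ocular table only), the severity table still holds participant counts, but the SAP does not say so.
- **Fellow eyes in Stage 1.** Section 2.2 makes the left eye the only study eye in Stage 1. The ocular category in section 8.2.1 takes in either eye. If study eyes are the denominator, an event in the undosed right eye enters the numerator but has no place in the denominator.

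This matters because section 3.5 keeps only adverse events and laboratory data for the synoptic report, and the two tables in section 8.2.3 are its only adverse event summaries by term. The product is an eye drop in its first human study, so ocular events are central to its safety profile.

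**Working it through.** The plan states no figure on this point, so there is nothing to reproduce. The check shows how far the possible counts can differ.

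**Inputs**
- 9 active and 3 vehicle participants per cohort (SAP section 2.2, Table 1).
- Vehicle pooled within each stage (SAP section 4.0): 3 × 3 = 9 vehicle participants in Stage 2a.
- Both eyes are study eyes in Stage 2a (SAP section 2.2): 9 × 2 = 18 study eyes per dose group and 18 in pooled vehicle.
- Numbers of events, laterality and severity are hypothetical. The 18-eye denominator is an assumption, because the SAP gives none.

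**Eyes over study eyes.** If *k* of 18 eyes are affected, the number of affected participants lies between ceil(*k*/2) (as many bilateral as possible) and min(*k*, 9) (as few bilateral as possible).

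| Eyes affected | Eye percentage | Fewest participants | Most participants |
|---|---|---|---|
| 6 | 6/18 = 33.3% | 3/9 = 33.3% | 6/9 = 66.7% |
| 9 | 9/18 = 50.0% | 5/9 = 55.6% | 9/9 = 100% |

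The gap is widest at 8 to 10 eyes, where it is 4/9 = 44.4 percentage points. An active group with six unilateral cases and a vehicle group with three bilateral cases both show 6/18 = 33.3% of eyes. Their participant incidences are 6/9 = 66.7% and 3/9 = 33.3%.

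**Choice of denominator.** Take 3 affected participants of 9, so 33.3% under the protocol rule whatever the laterality.
- Over 18 eyes: 3/18 = 16.7% (all unilateral) to 6/18 = 33.3% (all bilateral).
- Over 9 participants: 3/9 = 33.3% to 6/9 = 66.7%.
- Five bilateral cases over participants give 10/9 = 111.1%, which is not a valid incidence. The text does not exclude this calculation.

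**Severity table, reading A only.** Suppose 5 of 9 participants have bilateral events: 3 mild in both eyes, and 2 mild in one eye and moderate in the other.
- Protocol rule (worst severity per participant): 3/9 = 33.3% mild, 2/9 = 22.2% moderate.
- Eye count: mild 3 × 2 + 2 × 1 = 8, so 8/18 = 44.4%; moderate 2, so 2/18 = 11.1%.

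The moderate percentage is halved, and two participants appear in both rows.

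**Stage 1.** With one dosed eye per participant, dosed-eye counts over study eyes equal participant counts (3 affected is 3/9 = 33.3% either way). Only fellow-eye events are affected. If both eyes were put in the denominator, the same 3 would read 3/18 = 16.7%.

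**The case against.** The strongest reply has five parts.

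1. The protocol hands safety detail to the SAP, and counting by eye is permissible for drops given to both eyes. This stands. What remains is the undefined denominator and scope, and the missing entry in Table 3.
2. Reading B may be what was meant. Only one of the two tables is ocular, and the default of one count per subject fits the other. That is plausible, and then participant counts by ocular term survive in the severity table, split by severity. But the SAP does not say it, and the ocular table would still lack a denominator.
3. Other outputs fill part of the gap. Section 8.1 fixes the safety population for subject counts. Section 8.2.2 gives subject totals for any ocular TEAE, related TEAEs, serious TEAEs and TEAEs leading to discontinuation, and leaves room for more summaries. Those totals are not by term or severity, and the room for more is not a commitment. The protocol's by-participant listings would allow a recount and are not expressly withdrawn. However, the only adverse event listing the SAP names is in section 8.2.4: "Listings of TEAEs leading to discontinuation will be presented".
4. The illustrations rest on invented events and on 18 study eyes, which the SAP does not state. True. Section 2.2 makes study eyes the natural choice, and the alternative of dividing by participants is shown above and behaves worse. The Stage 1 mismatch likewise depends on choosing study eyes.
5. The stakes are modest. The study ended early for reasons unrelated to safety, no testing is planned, and data monitoring reviews followed a separate charter. This limits the point to how the results are reported.

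**Conclusion.** The concern holds. Followed as written, the SAP replaces the protocol's participant count with an eye count of undefined denominator, above two tables, without recording the change. On the literal reading, no SAP table gives Stage 2a participant incidence by ocular preferred term, and the severity table mixes units. On the narrower reading, that information survives in the severity table but the plan does not make this clear.

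The distortion can be large within a group: at the planned 9 participants and an assumed 18 study eyes, the same eye percentage is compatible with participant incidences up to 44 percentage points apart. The percentages rest on hypothetical events and on groups filled as planned. The textual gaps do not depend on either. The impact is limited to descriptive tables by preferred term, mainly in Stage 2a. This should be corrected before the tables are produced, but it does not threaten the study's conduct or any formal inference.

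**What to change.** Amend SAP section 8.2.3 as follows.

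- In the table by system organ class, preferred term and severity, count each subject once per preferred term, at the worst severity across both eyes, over safety-population subjects in the treatment group.
- In the ocular table by system organ class and preferred term, give subject counts on the same denominator.
- If eye counts are kept, put them in a separate, labelled supplement over study eyes (left eye in Stage 1, both eyes in Stage 2a), with Stage 1 fellow-eye events shown separately.
- Record any eye-level counting in section 12.1, Table 3.

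The cost is a few sentences of SAP text, one line in Table 3 and minor programming of two tables. No new data are needed.

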8.2.4 Adverse Events Leading to Study Treatment Discontinuation

Listings of TEAEs leading to discontinuation will be presented.

8.3 Analysis of Laboratory Data

Descriptive statistics for values and changes from baseline in standard units at each assessment timepoint will be summarized.

Clinical laboratory test values will be considered potentially clinically significant (PCS) if they meet either the lower-limit or higher-limit PCS criteria listed in Appendix B. The number and percentage of subjects who have at least one PCS postbaseline clinical

laboratory value will be tabulated. The denominator will be the number of subjects with available non-PCS baseline values and at least 1 postbaseline value. The numerator will be the number of subjects with available non-PCS baseline values and at least 1 PCS postbaseline value.

Subjects with PCS findings will be listed.

9.0 Pharmacokinetic Analyses

9.1 General Considerations

Descriptive statistics (arithmetic mean, standard deviation, relative standard deviation, maximum, median, minimum) will be reported for tear and plasma AGN-241622 concentration data at all timepoints by cohort, study intervention and study day.

Descriptive statistics (arithmetic mean, standard deviation, relative standard deviation, maximum, median, minimum) will be calculated for all PK parameters.

Analyses of plasma and tear PK will be performed for AGN-241622 treated subjects only. PK parameters will be calculated using standard Phoenix WinNonlin equations. AUC will be calculated by using the linear-log trapezoidal rule. In addition to the PK parameters listed in Section 9.2 and Section 9.3, additional parameters may be calculated, as necessary.

No formal statistical analysis of PK data will be performed.

9.2 Stage 1

Calculated plasma and tear PK parameters will include area under the concentration versus time curve from 0 to the last timepoint with measurable AGN-241622 concentrations (AUC_{0-t}), maximum observed concentration (C_{max}), and time to maximum observed concentration (T_{max}).

9.3 Stage 2a

Calculated PK parameters on Day 1 will include area under the concentration versus time curve from 0 to the end of the dosing interval ($AUC_{0-\tau}$), maximum observed concentration (C_{max}), and time to maximum observed concentration (T_{max}).

Steady state PK parameters calculated on Day 14 will include $AUC_{0-\tau,ss}$, $C_{max,ss}$, $T_{max,ss}$. Local and systemic accumulation will be assessed by calculating the accumulation index (AI) for AUC and C_{max} on Day 14.

Descriptive statistics will be used to summarize plasma trough concentrations on Days 2-7 and Day 14.

10.0 Interim Analyses

No interim analysis is planned.

10.1 Data Monitoring Committee

After Cohort 1, 2, 4, 5, and 6 are complete, an internal data monitoring committee (DMC) composed of individuals independent of 2011-101-013 study team at AbbVie and with relevant expertise in their field will review unmasked safety and plasma PK data, along with target engagement and efficacy data if necessary from the ongoing study, and will recommend if it is acceptable to proceed to the next planned cohort. The primary responsibility of the DMC will be to protect the safety of the subjects participating in this study.

A separate DMC charter describes the roles and responsibilities of the DMC members, frequency of data reviews, relevant data to be assessed, and general operations.

Since there are no efficacy analyses for early stopping, no alpha adjustment is needed.

11.0 Overall Type-I Error Control

Not applicable. No statistical testing is planned.

12.0 Version History

Table 2. SAP Version History Summary

Version	Date	Summary
1.0	05 Nov 2020	Initial version
2.0	21 Jun 2023	Updated due to Sponsor early discontinuation of the study
3.0	12 July 2023	Updated due to the change for a synoptic CSR

12.1 Changes to Planned Analyses in the Protocol

Due to the early discontinuation of the study after completion of Cohort 6, there will not be any subjects in Stage 2b, hence no Stage 2b related analysis will be conducted.

Changes from the originally planned statistical analysis specified in the protocol are outlined Table 3.

Table 3. Changes to Planned Analyses in the Protocol

Statistical Analysis Plan	Rationale for Changes

 No statistical analysis or outputs to be generated for Stage 2b or other objectives/endpoints Synoptic CSR will be provided. Only key safety analysis will be performed. 	Early study termination prior to Stage 2b

Appendix B. Potentially Clinically Important Criteria for Safety

The potentially clinically significant criteria for clinical laboratory parameters are provided in the following section.

Table B-1 Potentially Clinically Significant Criteria for Clinical Laboratory Parameters

Parameter	SI Unit	Lower Limit	Higher Limit
CHEMISTRY			
Albumin	g/L	< 0.8 x LLN	> 1.2 x ULN
Alanine aminotransferase	U/L		≥ 3.0 x ULN
Alkaline phosphatase	U/L		≥ 3.0 x ULN
Aspartate aminotransferase	U/L		≥ 3.0 x ULN
Bicarbonate	mmol/L	< 0.9 x LLN	> 1.1 x ULN
Bilirubin, total	μmol/L		≥ 1.5 x ULN
Blood urea nitrogen	mmol/L		> 1.5 x ULN
Calcium	mmol/L	< 0.9 x LLN	> 1.1 x ULN
Chloride	mmol/L	< 0.9 x LLN	> 1.1 x ULN
Cholesterol, total	mmol/L		> 1.6 x ULN
Creatinine	μmol/L		> 1.5 x ULN
Creatine kinase	U/L		> 2.0 x ULN
Estimated glomerular filtration rate	mL/min/1.73 m ²	< 0.8 x LLN	
Glucose, fasting	mmol/L	< 0.8 x LLN	> 2.0 x ULN
Phosphorus	mmol/L	< 0.9 x LLN	> 1.1 x ULN
Potassium	mmol/L	< 0.9 x LLN	> 1.1 x ULN
Protein, total	g/L	< 0.9 x LLN	> 1.1 x ULN
Sodium	mmol/L	< 0.9 x LLN	> 1.1 x ULN
Triglycerides	mmol/L		> 2.0 x ULN
Uric acid	μmol/L		> 1.2 x ULN
HEMATOLOGY			
Basophils, absolute cell count	10 ⁹ /L		> 2.0 x ULN

Parameter	SI Unit	Lower Limit	Higher Limit
Eosinophils, absolute cell count	10 ⁹ /L		> 2.0 x ULN
Hematocrit	Ratio	< 0.9 x LLN	> 1.1 x ULN
Hemoglobin	g/L	< 0.9 x LLN	> 1.1 x ULN
Lymphocytes, absolute cell count	10 ⁹ /L	< 0.7 x LLN	> 1.3 x ULN
Parameter	SI Unit	Lower Limit	Higher Limit
Monocytes, absolute cell count	10 ⁹ /L	< 0.5 x LLN	> 2.0 x ULN
Neutrophils, absolute cell count	10 ⁹ /L	< 0.7 x LLN	> 1.3 x ULN
Platelet count	10 ⁹ /L	< 0.5 x LLN	> 1.5 x ULN
Red blood cell count	10 ¹² /L	< 0.9 x LLN	> 1.1 x ULN
White blood cell count	10 ⁹ /L	< 0.9 x LLN	> 1.5 x ULN
URINALYSIS			
pH	pH	< 0.9 x LLN	> 1.1 x ULN
Glucose	-		Positive ^a
Protein	-		Positive ^b
Specific gravity			> 1.1 x ULN

LLN = lower limit of normal value; ULN = upper limit of normal value; normal value provided by laboratory; SI = Le Système International d'Unités (International System of Units)

- a. Any results other than negative will be considered as positive.
- b. Any results other than trace or negative will be considered as positive.

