3.5 Endpoint(s) to be analyzed for Synoptic CSR

Due to the early discontinuation of the Study after completion of Cohort 6, a synoptic CSR will be provided for this study, and only the endpoints 1 and 4 of Section 3.3 Safety Endpoints will be analyzed.

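### The PCS limit for urine specific gravity (> 1.1 x ULN) lies above 1.10 for any laboratory ULN, so this row's count is in effect zero before any data are seen

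*SAP*

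**What the plan says.** SAP Table B-1 lists PCS limits for chemistry, hematology and urinalysis, 34 rows in all. For "Specific gravity" the lower-limit cell is empty and the upper limit is > 1.1 x ULN. The footnote defines the reference limit as the "normal value provided by laboratory", and neither document gives a number for it.

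SAP Section 8.3 treats a laboratory value as PCS "if they meet either the lower-limit or higher-limit PCS criteria listed in Appendix B". It then tabulates the number and percentage of subjects with a PCS value after baseline: "The numerator will be the number of subjects with available non-PCS baseline values and at least 1 PCS postbaseline value". The denominator is subjects with a non-PCS baseline and at least one postbaseline value. Subjects with PCS findings are also listed.

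Protocol Section 9.4.2.2 leaves the PCS laboratory criteria to the SAP, so Table B-1 is the only source. Protocol Table 10-1 includes specific gravity in routine urinalysis. SAP Section 3.5 keeps the laboratory data in the reduced report: "only the endpoints 1 and 4 of Section 3.3 Safety Endpoints will be analyzed", and endpoint 4 is clinical laboratory assessments.

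**The concern.** A 10% margin over the upper normal limit is reasonable where zero is a natural origin, as for sodium, calcium or hemoglobin, which carry the same multiplier. Specific gravity has its origin at 1.000, the value for water, and only the excess over 1.000 carries information. Multiplying the whole value by 1.1 adds more than 0.10 to the limit, while the excess at the limit is itself only a few hundredths under the ULNs assumed below.

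What is at stake is how one line of a safety table reads. If no genuine reading can exceed the limit, no baseline can be PCS either. Every subject with a baseline and a postbaseline value then enters the denominator, and none can enter the numerator. The result looks like an observed absence of abnormal values, although the rule fixed it in advance.

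**Working it through.** **Inputs**

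- Multiplier 1.1, upper limit only: SAP Table B-1.
- ULN: supplied by the laboratory, not in the documents. Assumed here to be 1.020 to 1.040. The bound in step 1 does not need this assumption.
- Water = 1.000: the definition of specific gravity.
- Highest genuine urine reading: not in the documents. Assumed here to be 1.030 to 1.080.

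The plan states no numeric threshold, so there is no figure of its own to reproduce.

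**Step 1. Lower bound on the threshold.** Threshold = 1.1 x ULN. Since ULN > 1.000, the threshold > 1.1 x 1.000 = 1.10, whatever reference range the laboratory uses.

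**Step 2. Threshold for assumed ULNs.** The excess ratio is (1.1 x ULN - 1) / (ULN - 1), that is, how many times the excess at the ULN a reading must reach.

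| Assumed ULN | 1.1 x ULN | Excess needed | Excess at ULN | Ratio |
|---|---|---|---|---|
| 1.020 | 1.122 | 0.122 | 0.020 | 6.1 |
| 1.030 | 1.133 | 0.133 | 0.030 | 4.4 |
| 1.040 | 1.144 | 0.144 | 0.040 | 3.6 |

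**Step 3. Can it be reached?** A highest reading M exceeds the threshold only if ULN < M / 1.1.

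| Assumed highest reading M | ULN would have to be below |
|---|---|
| 1.030 | 0.936 |
| 1.050 | 0.955 |
| 1.080 | 0.982 |
| 1.100 | 1.000 |

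All of these require a ULN below that of water. The conclusion therefore holds for any highest reading up to 1.10 and does not depend on a particular choice within the assumed range.

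**Step 4. What the table would show.** Planned numbers are 9 active subjects per cohort. SAP Section 4.0 pools vehicle within each stage, giving 3 x 3 = 9. If all planned subjects have a baseline and a postbaseline value, the row is 0/9 in each of the three active groups and the pooled vehicle group, in both Stage 1 and Stage 2a.

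**The case against.** The strongest reply is that little depends on this row. It is one of 34 in a descriptive table. SAP Section 11.0 plans no statistical testing, and no decision rule uses the count. SAP Section 1.0 says that the study was stopped for reasons other than safety. Section 8.3 also does not say whether rows with zero counts will be printed. All of this stands, and it keeps the point minor. It does not make the criterion work.

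A reader might go further and infer that an abnormal specific gravity would go unseen because PCS counts are the only screen for laboratory abnormalities. The documents do not support that. SAP Section 8.3 plans descriptive statistics for values and changes from baseline at each timepoint. Protocol Section 8.2.4 and Appendix 2 require review of the laboratory results and entry of relevant changes as adverse events. Appendix 3 counts clinically significant urinalysis results as adverse events, and these are the other endpoint retained in SAP Section 3.5.

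A reader might also infer that the flag can never fire on any record. That is too strong in two ways. It needs an assumed highest urine value, which the documents do not give. A data-entry error, or a result and limit on different scales (1030 against 1.030), could still exceed the threshold.

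Finally, the empty lower-limit cell is not itself a defect. Alanine aminotransferase, creatinine, uric acid and other rows are also one-sided.

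**Conclusion.** The point holds as a minor defect in a stated rule. That the threshold exceeds 1.10 follows from the SAP's multiplier and the definition of specific gravity alone. That the flag cannot fire needs one further assumption, that genuine urine readings stay below 1.10. Every assumed maximum from 1.030 to 1.080 falls short of it. On that assumption the PCS count is 0/N in every group before any data are seen, and the PCS listing for this row is empty.

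The effect is confined to that count and listing. The descriptive summaries of specific gravity, the adverse event data and the other 33 rows of Table B-1 are unaffected.

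**What to change.** Change one cell of Table B-1, in one of two ways.

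1. Replace > 1.1 x ULN with > ULN for specific gravity. The limit is the laboratory's own and is set independently of the results. That matters because SAP version 3.0 was written after the study ended, and a newly chosen number could look post hoc. Add a footnote that this row is an out-of-range flag and less stringent than the other numeric rows, which mostly use a multiple beyond the normal limit. Under Section 8.3, subjects already above ULN at baseline would then leave the denominator, so N may differ from the other rows.
2. Delete the row, so that no predetermined 0% is reported. The descriptive statistics for specific gravity remain.

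Adding a lower limit is not needed to repair the defect. The cost is one table cell and one line of programming, plus a footnote under option 1. No further data are needed.
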